11.0 STATISTICAL CONSIDERATIONS

This is a single arm clinical trial to evaluate proton beam radiation therapy (PBT) for treatment of stage II/III esophageal cancer in two clinical settings; a.) definitive chemoradiation and b.) neoadjuvant chemoradiation followed by esophagectomy. While we will report and provide descriptive statistics between the two clinical settings, analyzing the differences is not our main concern. The main endpoints are to determine the patient-reported outcomes and physician-reported toxicities of proton beam therapy for esophagus cancer at 6 months. Additional endpoints in the setting of definitive chemoradiation are to assess the progression-free and overall survival

Protocol Version: 05/16/2023 Page 25 of 45

11.1 Sample Size

Due to the novel nature of this study, standard sample size and power calculations are not possible. Therefore, we plan to enroll 20 patients to both the operative and non-operative treatment arms (40 patients total) because we believe that we have the ability to accrue this number of patients in a timely and clinically relevant manner. This is NOT a randomized trial between these two therapy strategies. This number of patients is intended to obtain preliminary data upon which to base subsequent studies.

11.2 Toxicity Analysis

Although this is not a randomized trial where the number of patients on each treatment arm is controlled, we will capture that information and hope that these two groups will be relatively the same size. Early stopping rules would cease accrual to the trial if \geq Grade 4 CTCAEv4 gastrointestinal or pulmonary toxicity rates exceed 10% (2), or if \geq grade 3 CTCAEv4 gastrointestinal or pulmonary toxicity rates exceed 30% (6) for the first 20 patients enrolled. In order to assess the overall toxicity of this treatment method we will compare the proportion of \geq Grade 3 gastrointestinal or pulmonary toxicity events against historical controls utilizing Binomial tests for proportion.

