1.2 Radiation Therapy in the Treatment of Esophageal Cancer

Radiation modality has advanced substantially over the past two decades. Photon therapy (such as higher energy X-rays) is the most common radiation modality used for cancer treatment. Since the esophagus is located between critical structures such as the heart anteriorly, the spinal cord posteriorly, and the lungs on either side, substantial doses are usually delivered to the normal organs in order to treat the tumor adequately. The current use of photon-based technology is called Intensity Modulated Radiation Therapy (IMRT), where each beam (typically 5-7) can be further modulated using computer-controlled multi-leaf collimators to dynamically block the path of the radiation while the beam is on, which effectively allows the dose to be "painted" with various intensities allowing greatest dose conformality to the tumor and dose avoidance to the normal structures. However, despite the advantages of IMRT, it is not considered a standard technique in routine clinical trials since it takes great expertise in the planning and quality assurance (QA) process. At Washington University, we have been using IMRT for treatment of esophageal cancer patients since 2006. Many of our patients receiving definitive chemoradiation therapy have been treated on our prospective clinical trial for locally-advanced esophagus cancer (HRPO# 201105449 / 06-1070). Our accrual to this trial was slow, mainly because most of our patients receive trimodality therapy (chemoradiation followed by surgery). Nevertheless, this form of photon therapy has been well-tolerated for this inoperable patient population.

There have been several trials evaluating the effectiveness and toxicity of photons in the management of esophagus cancer. A comprehensive review by Monjazeb and Blackstock summarizes toxicity risk for patients receiving chemoradiation alone or chemoradiation

Protocol Version: 05/16/2023 Page 7 of 45

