5.2.1 Dose Specifications

The daily prescription dose will be 1.8 or 2 Gy RBE ("Relative Biologic Equivalence"), at the discretion of the treating radiation oncologist, to be delivered to the periphery of the planning target volume (PTV). The isodose line (generally 93-98%) chosen will encompass at least 95% of the PTV.

The maximum point dose, minimum point dose, and mean dose to PTV will also be reported.

a.) For patients with unresectable esophagus cancer, the total dose will be 60 Gy (RBE) (at 2 Gy/Fx/day) or 59.4 Gy (RBE) (at 1.8 Gy/Fx/day) to PTV2. All doses will be prescribed to the periphery of PTV2. PTV1 will receive 50.4 Gy (RBE) (at 1.8 Gy/Fx/day) or 50 Gy (RBE) (at 2 Gy/Fx/day). PTV1 will encompass volumes that are not apparently involved based on PET/CT and/or EUS, but where pathological involvement risk is >20%.

Protocol Version: 05/16/2023 Page 15 of 45

b.) For patients with resectable esophagus cancer, the total dose will be 50 Gy (RBE) (at 2 Gy/Fx/day) or 50.4 Gy (RBE) at (1.8 Gy/Fx/day) to PTV1. All doses will be prescribed to the periphery of the PTV.

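### The stopping limits cover only the first 20 patients with both dose settings pooled, so one setting can exceed a limit unnoticed and no numeric limit applies after patient 20

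*Combined protocol and SAP*

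**What the plan says.** Section 11.2 has one rule for the whole trial: "Early stopping rules would cease accrual to the trial if" grade 4 or worse "gastrointestinal or pulmonary toxicity rates exceed 10% (2"), or if grade 3 or worse "gastrointestinal or pulmonary toxicity rates exceed 30% (6) for the first 20 patients enrolled". Neither limit is tied to a setting. The same section notes that "this is not a randomized trial where the number of patients on each treatment arm is controlled" and only hopes that the two groups will be of similar size.

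Section 5.2.1 gives the settings different total doses: "For patients with unresectable esophagus cancer, the total dose will be 60 Gy (RBE"), or 59.4 Gy at 1.8 Gy per fraction; and "For patients with resectable esophagus cancer, the total dose will be 50 Gy (RBE"), or 50.4 Gy at 1.8 Gy per fraction. Section 11.1 sets the size: "we plan to enroll 20 patients to both the operative and non-operative treatment arms (40 patients total"). Section 10.0 asks for toxicity by cohort in the semi-annual report to the QASMC but attaches no threshold or action to it.

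**The concern.** A pooled count averages a toxic setting with a quiet one. The settings differ in dose and in operability. Section 1.2 also reports that many patients in the site's earlier 60 Gy trial died of intercurrent illness linked to comorbidity or age. The mix within the first 20 is left to chance. Section 1.2 says that "most of our patients receive trimodality therapy (chemoradiation followed by surgery"), so a first 20 with few definitive patients is possible.

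The second gap is in time. The rule looks at 20 of 40 patients. If one setting accrues slowly, most of its patients enrol after the only numeric check has passed. What is at stake is timely recognition of excess severe toxicity in one setting.

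**Working it through.** **Inputs.** Limits of 10% and 30% on the first 20 enrolled (Section 11.2); 20 planned per setting (Section 11.1); split uncontrolled (Section 11.2), taken here as 10:10 with 5:15, 8:12 and 12:8 as the range. The documents give no expected rate by setting for this composite, so all true rates below are assumptions.

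**1. The plan's own counts.** 0.10 × 20 = 2 and 0.30 × 20 = 6, matching the bracketed figures. Read literally, *exceed* means the rule trips at 3 grade 4+ or 7 grade 3+ patients.

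**2. Highest rate in one setting that does not trip the rule.** With n of the first 20 in that setting and no events in the other, the ceilings are min(2, n)/n and min(6, n)/n.

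| Split (n : other) | Grade 4+ ceiling | Grade 3+ ceiling |
|---|---|---|
| 5:15 | 2/5 = 40% (4.0×) | 5/5 = 100% (3.3×) |
| 8:12 | 2/8 = 25% (2.5×) | 6/8 = 75% (2.5×) |
| 10:10 | 2/10 = 20% (2.0×) | 6/10 = 60% (2.0×) |
| 12:8 | 2/12 = 16.7% (1.67×) | 6/12 = 50% (1.67×) |

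One event in the other setting lowers the 10:10 ceilings to 1/10 = 10% (1×) and 5/10 = 50% (1.67×). If the bracketed 2 and 6 are themselves the triggers, the 10:10 ceilings with no events elsewhere are also 10% and 50%.

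**3. Patients beyond the rule.** At 10:10, 20 − 10 = 10 planned patients per setting enrol after patient 20. At 5:15, 20 − 5 = 15 of the smaller setting's 20 do so.

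**4. Grade 3+ limb alone, assumed 50% in the definitive and 15% in the pre-operative setting.** The pooled count is Bin(n, 0.5) + Bin(20 − n, 0.15), and the rule trips at 7.
- 10:10: 0.49. 5:15: 0.16.
- Same limit on the definitive setting's own 20: P(Bin(20, 0.5) ≥ 7) = 0.94.
- Same limit when only ten definitive patients have been seen: P(Bin(10, 0.5) ≥ 7) = (120 + 45 + 10 + 1)/1024 = 0.17. With five seen, 7 events cannot occur.

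Over the first ten definitive patients, the separate limit (0.17) is therefore weaker than the pooled rule at 10:10 (0.49). The rise to 0.94 comes from patients 11 to 20 of that setting. P(Bin(13, 0.5) ≥ 7) = 0.50, so even odds of a crossing are reached only at its 13th patient.

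**5. Both limbs, adding assumed grade 4+ rates of 15% and 5%.** Grade 4+ patients are a subset of grade 3+ patients: given x of the latter, the former are Bin(x, p4/p3). Either limb can trip.
- Pooled rule: about 58% at 10:10 and 27% at 5:15.
- Pooled rule plus 3 or more (grade 4+) or 7 or more (grade 3+) in either setting's 20: about 96% at either split.

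The contrast shrinks if the other setting is less quiet. On the grade 3+ limb, with 50% against 25%, the pooled rule fires 68% (10:10) and 44% (5:15). With 50% against 30%, it fires 76% and 59%.

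**6. Unwanted pauses, both limbs, equal true rates in both settings.**

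| Grade 3+ / grade 4+ | Pooled only | With added limits |
|---|---|---|
| 15% / 5% | 9% | 20% |
| 20% / 5% | 14% | 30% |
| 30% / 10% (at the limits) | 51% | 80% |

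**The case against.** This is a 40-patient preliminary study, and Section 11.0 says differences between settings are not its main concern. Section 10.0 requires ongoing monitoring of serious toxicity and cohort summaries to the QASMC, and Section 5.6 lets the centre close the study. Oversight by setting therefore exists, but without a number that triggers action.

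Three stronger readings are tempting, and the documents do not support them.
- *A setting at twice the limit will pass.* It can pass, but at 10:10 only if the other setting has no events. At a 15% true grade 3+ rate there, that has probability 0.85^10 = 0.20.
- *The 60 Gy setting is known to be the more toxic one and will be scarce in the first 20.* No rates by setting are given, and Section 1.2 calls the site's 60 Gy IMRT experience well tolerated, though that was photons and this trial uses protons. The remark about trimodality therapy makes a 5:15 split possible, but Section 11.1 plans 20 in each setting.
- *Splitting the first 20 by setting is what raises detection.* Step 4 shows otherwise. Early clusters of 6/10 or 5/5 (grade 3+) and 2/10 or 2/5 (grade 4+) would still not trip the added limits.

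The objection on cost also stands: the added limits roughly double the chance of a pause when rates are acceptable.

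**Conclusion.** The point holds in a bounded form. On the literal reading of *exceed*, a setting with 10 or fewer of the first 20 patients can reach two or more times a stated limit without tripping the rule when the other setting has few or no events; with 12 of the 20 the ceiling is 1.67 times. After patient 20 nothing numeric applies, and this is the larger weakness. The 58% and 27% against 96% rest on assumed rates with one quiet setting, and they measure the value of following each setting through its 20 patients. The result also assumes that the first 20 means the first 20 in the trial, as the reference to trial accrual suggests. If 20 per setting was meant, the pooling problem disappears, but Section 11.2 would need to say so.

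**What to change.** In Section 11.2, keep the pooled check and also apply the plan's own limits to each setting's planned 20 patients: 3 or more with grade 4+, or 7 or more with grade 3+, counted as events occur. A crossing would pause accrual to that setting for QASMC review. State whether the bracketed 2 and 6 are the triggers or the last allowed counts, and align the per-setting counts with that answer. Report the stopping probabilities for both limbs together, over a range of rates and splits.

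The cost is a few sentences of protocol text, since toxicity by cohort already goes to the QASMC, plus the extra pauses in step 6. The consequence of a crossing is a review in one setting, not closure of the trial. The sponsor should accept that trade-off knowingly, and should not present the change as protection against small early clusters.

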5.6 Duration of Therapy

If at any time the constraints of this protocol are considered to be detrimental to the patient's health and/or the patient no longer wishes to continue protocol therapy, the protocol therapy should be discontinued and the reason(s) for discontinuation documented in the case report forms.

In the absence of treatment delays due to adverse events, PBT may continue for 6 weeks and QOL assessments for one year after the end of CRT or until one of the following criteria applies:

- Documented and confirmed disease progression
- Death
- Adverse event(s) that, in the judgment of the investigator, may cause severe or permanent harm or which rule out continuation of study drug
- General or specific changes in the patient's condition render the patient unacceptable for further treatment in the judgment of the investigator
- Suspected pregnancy
- Serious noncompliance with the study protocol (if the patient is noncompliant with their recommended treatment, rendering his/her QOL data not usable)
- Lost to follow-up
- Patient withdraws consent
- Investigator removes the patient from study
- The Siteman Cancer Center decides to close the study

5.7 **Duration of Follow-up**

Follow-up visits are typically done at intervals of 3-4 months for the first 2 years after completion of last treatment procedure, and every 4-6 months thereafter for the next 3 years.

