10.0 DATA AND SAFETY MONITORING

In compliance with the Washington University Institutional Data and Safety Monitoring Plan, the Principal Investigator will provide a Data and Safety Monitoring (DSM) report to the Washington University Quality Assurance and Safety Monitoring Committee (QASMC) semi-annually beginning six months after accrual has opened (if at least five patients have been enrolled) or one year after accrual has opened (if fewer than five patients have been enrolled at the six-month mark).

The Principal Investigator will review all patient data at least every six months, and provide a semi-annual report to the QASMC. This report will include:

- HRPO protocol number, protocol title, Principal Investigator name, data coordinator name, regulatory coordinator name, and statistician
- Date of initial HRPO approval, date of most recent consent HRPO approval/revision, date of HRPO expiration, date of most recent QA audit, study status, and phase of study
- History of study including summary of substantive amendments; summary of accrual suspensions including start/stop dates and reason; and summary of protocol exceptions, error, or breach of confidentiality including start/stop dates and reason
- Study-wide target accrual and study-wide actual accrual
- Protocol activation date
- Average rate of accrual observed in year 1, year 2, and subsequent years
- Expected accrual end date and accrual by cohort
- Objectives of protocol with supporting data and list the number of participants who have met each objective
- Early stopping rules with supporting data and list the number of participants who have met the early stopping rules
- Summary of toxicities separated by cohorts
- Abstract submissions/publications
- Summary of any recent literature that may affect the safety or ethics of the study

The study principal investigator and Research Patient Coordinator will monitor for serious toxicities on an ongoing basis. Once the principal investigator or Research Patient Coordinator becomes aware of an adverse event, the AE will be reported to the HRPO and QASMC according to institutional guidelines.

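### The numeric toxicity stopping rule covers only the first 20 of 40 planned patients; patients 21-40 have monitoring but no binding count

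*Combined protocol and SAP*

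**What the plan says.** Section 11.2 has two limits, and crossing either ceases accrual to the trial. Grade 4 or higher must not have "gastrointestinal or pulmonary toxicity rates exceed 10% (2"), and grade 3 or higher must not have "gastrointestinal or pulmonary toxicity rates exceed 30% (6) for the first 20 patients enrolled". Section 11.1 sets the size: "we plan to enroll 20 patients to both the operative and non-operative treatment arms (40 patients total").

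Section 10.0 continues throughout the study: "The study principal investigator and Research Patient Coordinator will monitor for serious toxicities on an ongoing basis", and "The Principal Investigator will review all patient data at least every six months, and provide a semi-annual report to the QASMC". That report must list the early stopping rules with supporting data and summarise toxicities by cohort. Section 5.6 includes, among the reasons to end protocol participation, "The Siteman Cancer Center decides to close the study". Neither section adds a number. The binomial comparison with historical controls in section 11.2 is an overall analysis, not a stopping rule.

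**The concern.** A trial that just passes at patient 20 can run to 40 with toxicity above the sponsor's own 10% or 30% without meeting any written rule. The monitoring committee would see the counts and would have the two percentages as reference values, but nothing says that they still bind. Whether to stop would then be argued case by case, with the data already in view, for half of the planned patients.

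**Working it through.** **Inputs.** Limits of 10% (2) and 30% (6) and the first 20 patients come from section 11.2; 40 patients come from section 11.1. All true toxicity rates below are assumptions.

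**The plan's own counts.** 0.10 × 20 = 2 and 0.30 × 20 = 6, so the printed figures reproduce with a denominator of 20. With 40 they would be 4 and 12. The phrase about the first 20 patients stands next to the grade 3+ limb only, but the count of 2 shows that the grade 4+ limb uses 20 as well. The rule covers 20/40 = 50% of planned patients.

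**Triggers.** Reading the verb strictly, a rate exceeds the limit at these counts:

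| Patients | Grade 4+ (>10%) | Grade 3+ (>30%) |
|---|---|---|
| 20 | 3 or more | 7 or more |
| 30 | 4 or more | 10 or more |
| 40 (reference only) | 5 or more | 13 or more |

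**Miss at 20.** With X ~ Bin(20, p), the grade 4+ miss is P(X ≤ 2).
- p = 0.15: 0.0388 + 0.1368 + 0.2293 = 0.4049.
- p = 0.20: 0.0115 + 0.0576 + 0.1369 ≈ 0.2061 (terms rounded).
- Grade 3+, p = 0.40: P(X ≤ 6) = 0.2500.

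**Pass at 20, then above the limit at 40.** With Y ~ Bin(20, p) for the next 20 patients, sum P(X = x) × P(Y ≥ 5 − x) over x = 0, 1, 2.
- p = 0.15: 0.0388 × 0.1702 + 0.1368 × 0.3523 + 0.2293 × 0.5951 = 0.1913.
- p = 0.20: 0.0115 × 0.3704 + 0.0576 × 0.5886 + 0.1369 × 0.7939 = 0.1469.
- Grade 3+, p = 0.40 (13 or more of 40): 0.1545.

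These are shares of all trials.

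**Effect of one look at 30.** With Z ~ Bin(10, p), the extra stopping is the sum of P(X = x) × P(Z ≥ 4 − x).
- p = 0.15: 0.0388 × 0.0500 + 0.1368 × 0.1798 + 0.2293 × 0.4557 = 0.1310, so the miss is 0.4049 − 0.1310 = 0.274.
- p = 0.20: extra stopping 0.1054, so the miss is 0.2061 − 0.1054 = 0.101.
- Grade 3+, p = 0.40: extra stopping 0.1108, so the miss is 0.2500 − 0.1108 = 0.139.

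**Both limbs together.** Here each patient has grade 4+, grade 3 only, or neither (trinomial). Average enrolment is 20 × P(stop at 20) + 30 × P(stop at 30) + 40 × P(no stop).

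| True grade 3+ / grade 4+ | P(stop), look at 20 | P(stop), 20 and 30 | Mean enrolment, 20 | Mean enrolment, 20 and 30 |
|---|---|---|---|---|
| 16% / 5% | 9.3% | 11.6% | 38.1 | 37.9 |
| 30% / 10% | 50.8% | 62.0% | 29.8 | 28.7 |
| 40% / 20% | 88.1% | 95.2% | 22.4 | 21.7 |

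For 30%/10%: 20 × 0.508 + 40 × 0.492 = 29.8, and 20 × 0.508 + 30 × 0.112 + 40 × 0.380 = 28.7.

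**The case against.** A safety gate on the first cohort, followed by committee oversight, is a recognisable choice for a small trial that section 11.1 describes as a source of preliminary data. Most very toxic trials already stop at 20, and the added look saves about one patient per trial or fewer. It also makes stopping more likely for a treatment that sits exactly at the tolerated rates. All of this stands, and it limits the weight of the point. It does not supply a count for patients 21-40.

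The enrolment baseline is also open to challenge. Section 11.2 does not say that the rule is applied only once, at patient 20. If a third grade 4+ or seventh grade 3+ event stopped accrual as soon as it occurred, with immediate ascertainment, mean enrolment under the present rule would be 27.2 rather than 29.8 at 30%/10%, and 15.4 rather than 22.4 at 40%/20%. The miss probabilities would not change.

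If the printed 2 and 6 are meant as triggers, the misses at 20 shrink to 17.6%, 6.9% and 12.6%. They do not vanish, and that reading too ends at patient 20.

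A reader might infer two stronger claims that the documents do not support. One is that patients 21-40 go unmonitored; section 10.0 says otherwise. The other is that the first 20 will be mostly operative, so that definitive-setting patients largely escape the rule. Section 1.2 does say "Our accrual to this trial was slow, mainly because most of our patients receive trimodality therapy (chemoradiation followed by surgery"), and section 5.2.1 sets total dose by setting ("For patients with unresectable esophagus cancer, the total dose will be 60 Gy (RBE") for the unresectable group). But the remark in section 1.2 explains slow accrual to a previous IMRT trial and does not project the order of enrolment here. Section 11.1 plans 20 per setting and section 11.2 hopes for similar sizes. A pooled later look would not set a limit by setting in any case.

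**Conclusion.** The gap is real: the only numeric stopping rule ends at patient 20 of 40, and what follows rests on judgement. The change is worth making, but its benefit is modest and lies in the trials that pass at 20.

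The size depends on assumed true rates, on the strict reading of the limits, and on toxicity status being known at each look. Section 9.1 also counts toxicity beyond 90 days from the start of radiation, which may not be known at a look, so real detection could be lower.

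The shares that end above the limit should be quoted over all trials (19.1%, 14.7%, 15.5%). Taken only among trials that pass at 20 they look larger (47.2%, 71.3%, 61.8%), and a reader might mistake those for the overall risk. They also describe the position at patient 40, when accrual is over, so they measure the gap and not what a rule could prevent.

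**What to change.** In section 11.2, state that the same two percentages apply at one or more pre-specified later looks while accrual is open, with the timing left to the sponsor. At patient 30, for example, accrual would cease at 4 or more grade 4+ or 10 or more grade 3+. In the same edit, print the integer triggers for every look (at 20, under the strict reading, 3 or more and 7 or more), because the bracketed 2 and 6 can be read either as tolerated or as stopping counts. It would also help to say which toxicity window counts at a look, and that patients after the last look rely on section 10.0.

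The cost is a few sentences and more frequent stopping. With the look at 30, either-limb stopping rises by 2.3 percentage points at 16%/5% (9.3% to 11.6%) and by 11.2 points at 30%/10% (50.8% to 62.0%). If the sponsor prefers to keep a first-cohort gate only, section 11.2 should say so and name section 10.0 as what governs patients 21-40.
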